9.6. Data Management

Data for this study will be stored and extracted from the VHA database (previously described in Section 9.4) that contains information about patient demographics, vaccinations,

procedures, diagnoses, and death. Personal data will reside on VHA servers only and will not be transferred off the VHA servers to third parties (see Section 10.1 for further details).

9.6.1. Case Report Forms (CRF)

As used in this protocol, the term CRF should be understood to refer to either a paper form or an electronic data record or both, depending on the data collection method used in this study.

For case validation/adjudication via the medical records review study component, a CRF will be used to abstract data from VA CDW EHRs, as necessary, for atrial fibrillation cases among individuals vaccinated with ABRYSVO who are identified in the safety analyses (see Section 9.7.2.4 for further details). CRFs will include the encrypted study ID and will not contain any identifiable information. A CRF is required and should be completed for each included patient described above. The completed original CRFs will not be made available in any form. The CRF will consist of two parts: (1) a chart review CRF that will be populated based on a direct extraction of relevant information from the VA CDW for review by the adjudicators; (2) an adjudication page that will be completed by an adjudicator after reviewing data in the completed CRFs. The VA shall ensure that the CRFs are securely stored at White River Junction VA in encrypted electronic and/or paper form and will be password protected or secured in a locked room to prevent access by unauthorized third parties.

The VA has ultimate responsibility for the collection and reporting of all clinical, safety, and laboratory data entered on the CRFs and any other data collection forms (source documents) and ensuring that they are accurate, authentic/original, attributable, complete, consistent, legible, timely (contemporaneous), enduring, and available when required. The CRFs must be signed by the VA or by an authorized staff member to attest that the data contained in the CRFs are true. Any corrections to entries made in the CRFs or source documents must be dated, initialed, and explained (if necessary) and should not obscure the original entry.

The source documents are the hospital or the physician's chart. In these cases, data collected on the CRFs must match those charts.

9.6.2. Record Retention

To enable evaluations and/or inspections/audits from regulatory authorities or Pfizer, Analysis Group agrees to keep all study-related records, which includes study documents and deliverables such as the protocol, SAP, aggregated results tables, Statistical Analysis System (SAS) programming files, and study report. The records should be retained by Analysis Group according to local regulations or as specified in the vendor contract, whichever is longer. Analysis Group must ensure that the records continue to be stored securely for so long as they are retained.

If Analysis Group becomes unable for any reason to continue to retain study records for the required period, Pfizer should be prospectively notified. The study records must be transferred to a designee acceptable to Pfizer.

Study records must be kept for a minimum of 15 years after completion or discontinuation of the study, unless Analysis Group and Pfizer have expressly agreed to a different period of

retention via a separate written agreement. Record must be retained for longer than 15 years if required by applicable local regulations.

Analysis Group must obtain Pfizer's written permission before disposing of any records, even if retention requirements have been met.

9.7. Data Analysis

Detailed methodology for summary and statistical analyses of data collected in this study will be documented in an SAP, which will be dated, filed, maintained by the sponsor, and submitted to the Agency. The SAP may modify the plans outlined in the protocol; any major modifications of primary endpoint definitions or their analyses will be reflected in a protocol amendment.

All analyses will be conducted separately among individuals at least 60 years of age and among individuals 18-59 years of age. Pooled analyses among adults 18 years of age and older may be conducted using combined individual-level data from both age groups. Baseline characteristics will be descriptively compared and heterogeneity in the estimated incidence rates of atrial fibrillation among the 18-59 years old and 60 years and older age groups will be assessed using a two-population test (eg, Fisher's exact test or Z-test). If significant heterogeneity is observed with respect to patient characteristics (other than age) and incidence rate estimates, then no pooled analyses will be conducted. Otherwise, if heterogeneity is not observed and characteristics are considered to be sufficiently similar, then individual-level data from both age groups will be combined, and the descriptive analyses of characteristics and outcomes will be conducted using the combined dataset. If sample size is sufficient to allow comparative cohort analyses to be performed separately among individuals 18-59 years of age and individuals 60 years and older, then comparative analyses will also be performed in the pooled population. Further details will be provided in the SAP.

Data analyses will be conducted using SAS Enterprise Guide version 7.1 (SAS Institute Inc., Cary, NC) or R Version 3.5.3 or its latest version (R Core Team, Vienna, Austria).

9.7.1. Baseline Characteristics

Baseline demographics and clinical characteristics for individuals administered ABRYSVO, contemporary vaccinated controls, and contemporary unvaccinated controls will be summarized using descriptive statistics, consisting of the mean, standard deviation (SD), median, and interquartile range [IQR] values for continuous variables and frequency distributions for categorical variables. Standardized differences will be calculated between individuals who received ABRYSVO and contemporary vaccinated controls, and between individuals who received ABRYSVO and contemporary unvaccinated controls. Standardized differences <10% will indicate that the characteristics between recipients of ABRYSVO and the comparator cohort are balanced.

Descriptive statistics will also be used to summarize ABRYSVO characteristics, including calendar year and month of vaccination and care setting of vaccination (eg, OP clinic, pharmacy, IP ward).

9.7.2. Safety Analyses

Several analyses corresponding to the internal comparator cohort and SCRI designs will be conducted to evaluate safety events associated with ABRYSVO. Analyses will be conducted among all individuals meeting the study eligibility criteria.

Incidence rates for the primary and secondary outcomes will be compared to rates observed in the following control groups:

- Internal comparator cohorts: two random samples of contemporaneous vaccinated and unvaccinated matched controls in the VHA system.
- Self-controls: cases who experience safety events following vaccination using the SCRI design to compare the risk interval following vaccination to post-vaccination non-risk intervals in the same individual.

9.7.2.1. Incidence Rates of Safety Events

Incidence rates per 1,000 patient-years (and corresponding 95% CIs) will be calculated for atrial fibrillation and supraventricular arrhythmia observed in the risk interval as the total number of incident events divided by the total observation time.

9.7.2.2. Comparison with Contemporary Controls

Average treatment effect among the treated (ATT) weighting will be used to ensure baseline comparability between the ABRYSVO vaccinated cohort vs. contemporary vaccinated control cohort and between the ABRYSVO vaccinated cohort vs. contemporary unvaccinated control cohort. ATT weighting creates a "pseudo-population" in which the distribution of covariates is, on average, the same in each cohort. ⁶⁸ Specifically, ATT weights will be calculated to allow for estimation of the average treatment effect among individuals receiving ABRYSVO.⁶⁹ This approach will be taken to ensure that inference from the analysis will be applicable to this population. Individuals receiving ABRYSVO will receive an ATT weight of one. Individuals not receiving ABRYSVO will receive an ATT weight equal to the odds of receiving ABRYSVO conditional on their demographic and clinical characteristics as of the index date, which will be calculated based on the propensity score (PS). The PS is defined as an individual's probability of receiving ABRYSVO, conditional on observed baseline covariates, and will be calculated using a logistic regression model. The logistic regression model will include the cohort variable (ie, ABRYSVO vs. vaccinated or unvaccinated control) as the dependent variable, and the independent variables will include variables deemed clinically important and baseline covariates that have standardized differences ≥10% between the two cohorts. Specifically, ATT weights will be PS/(1-PS) for individuals with no record of ABRYSVO. The distribution of weights will be examined to assess extreme values, and truncation will be considered if necessary.

Weighted Cox regression with robust standard errors to account for within-subject correlation will be conducted to compare the risk of safety events between cohorts. Hazard ratios and corresponding 95% CIs will be summarized.

9.7.2.3. SCRI Design using the Conditional Poisson Regression for Comparison to Post-vaccination Control Intervals

SCRI design with post-vaccination control time period will include cases (ie, individuals vaccinated with ABRYSVO who experience safety events following vaccination) who have at least 41 days (or 38 days or 91 days for secondary analysis) of enrollment post-index to compare the incidence of safety events occurring in the risk interval following vaccination with the incidence of safety events occurring during the post-vaccination control interval.

A conditional Poisson regression model will be used to compare the rates of safety events in the risk interval vs post-vaccination control time period. From this model, we will report rate ratios and 95% CIs that will be interpretated as the relative incidence for the safety event in the risk interval compared to the control interval.

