The risk intervals were selected based on published literature and biological plausibility. ¹⁰⁻¹⁷ A safety event will be counted if it can be assigned to 1) the risk interval following ABRYSVO, 2) the post-vaccination control interval (SCRI design), or 3) risk interval for the contemporary vaccinated or unvaccinated controls.

The risk intervals for outcome evaluation for contemporary vaccinated or unvaccinated controls will be the same as for individuals who received ABRYSVO.

• Key Covariates: Baseline demographic (ie, age, sex, race/ethnicity, VHA service area, marital status) and clinical characteristics (ie, smoking, body mass index [BMI], history of anaphylaxis/allergic reactions including to vaccine components, history of hospitalizations, frailty index, Charlson Comorbidity Index [CCI], alcohol abuse, prior infections, history of atrial fibrillation prior to the baseline period, selected comorbidities, selected concomitant medications, history of immunizations, and coadministered immunizations). The final list of baseline characteristics will be defined in the statistical analysis plan (SAP) based on feasibility and availability.

Subgroups:

The following subgroups will be analyzed for the 18-59 years old age group and the 60 years and older age group:

- o Individuals in VA priority group 1;
- o Females enrolled in the VHA (pending sufficient sample size);
- O Individuals with co-administration with other vaccines (ie, influenza vaccine, COVID-19 vaccine, or other pre-specified vaccines [eg, shingles, hepatitis B]) on the same day.¹⁸

The following subgroups will be analyzed for the 60 years and older age group only:

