9.2.1. Inclusion Criteria

Three cohorts will be defined for the main analyses.

- A. A cohort of individuals who received ABRYSVO will form the ABRYSVO cohort and must have:
 - A record for at least one dose of ABRYSVO in the study period from 31 May 2023 (or earliest date of vaccine availability for the indicated population) to 31 May 2026; the date of ABRYSVO vaccination will define the index date for this cohort
 - o No record of an RSV vaccine from a manufacturer other than Pfizer
- B. A cohort of individuals who did not receive ABRYSVO but received another vaccine will form the contemporary vaccinated control cohort and must have:
 - A record for another vaccine (eg, influenza vaccine, COVID-19 vaccine, and other pre-specified vaccines such as shingles, hepatitis B listed in Section 9.3.3) within 30 days of a corresponding ABRYSVO vaccinee's vaccination date; the control's index date will be the date of the control's non-RSV vaccine
 - No record for any RSV vaccine on the index date or in the baseline period (ie, 2 years prior to the index date)
 - Individuals in the vaccinated control cohort who go on to receive an RSV vaccine following their index date will be censored at the time of RSV vaccination. If the RSV vaccine is ABRYSVO, these individuals will contribute to the ABRYSVO cohort starting from the date of ABRYSVO receipt.
- C. A cohort of individuals who did not receive ABRYSVO or another vaccine on the index date but had at least one vaccination record in the year prior to the index date will form the contemporary unvaccinated control cohort and must have:
 - No record for any RSV vaccine on or within 30 days of the index date or in the baseline period (ie, 2 years prior to the index date)

- No record for any other vaccine (eg, those listed in Section 9.3.3) on or within 30 days of the index date
 - This cohort will be assigned an index date matched to a corresponding ABRYSVO vaccinee's vaccination date. If the vaccination is associated with a healthcare encounter (ie, inpatient [IP] or outpatient [OP] visit), the unvaccinated control will be required to have a healthcare encounter within 30 days of the assigned index date, and the date of the healthcare encounter will be set as the index date for the unvaccinated control.

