 - HIV/Acquired immunodeficiency syndrome (AIDS)§
 - Moderate or severe primary immunodeficiency§
 - Rheumatologic/inflammatory conditions
 - Other immune deficiencies
- o Neurological/neuromuscular
 - Dementia (ie, Alzheimer's disease and related disorders, senile dementia)
 - Neurological disease
 - Neurologic or neuromuscular conditions causing impaired airway clearance or respiratory muscle weakness*§
 - Other neurologic diseases
- Respiratory
 - Asthma[§]
 - Chronic bronchiectasis
 - COPD/interstitial lung disease/emphysema§
 - Cystic fibrosis§

- Obstructive sleep apnea
- Pneumonia
- Other
 - Cancer
 - Chronic kidney disease/dialysis§
 - Diabetes mellitus without complications
 - Diabetes mellitus with complications§
 - Down syndrome
 - End-stage renal disease§
 - Gout
 - Hyperlipidemia
 - Hyperthyroidism (excluding autoimmune thyroiditis)
 - Illicit drug use (eg, cocaine)
 - Severe obesity (BMI ≥40 kg/m²)§
 - Stimulant use (eg, amphetamines, caffeine)
 - Metabolic syndrome
 - Panic disorders
 - Reaction to stress
- Concomitant medications[†]
 - Antineoplastic (ie, 7-con-o-methylnogaril, aclacinomycin a, cisplatin, doxorubicin, etaracizumab, ifosfamide, melphalan, mitoxantrone, trastuzumab)
 - o Bisphosphonates (ie, alendronate)
 - o Cardiovascular (ie, adenosine, dobutamine)
 - o Central nervous system (ie, clozapine, morphine)
- Other medications/procedures (identified outside of the American Heart Association [AHA] criteria)
 - o Nonsteroidal anti-inflammatory drugs (NSAID)
 - o Ivabradine
 - o Respiratory (ie, theophylline)
 - o Digitalis
 - CAR T-cell therapy*§
- History of immunizations
 - Seasonal influenza vaccine
 - o COVID-19
 - Tetanus diphtheria and pertussis (tetanus diphtheria and acellular pertussis vaccine [Tdap] or tetanus diphtheria and pertussis vaccine [Td])
 - o Chickenpox (varicella)
 - o Shingles (herpes zoster recombinant and/or live)
 - Human papillomavirus (HPV)
 - o Pneumococcal conjugate
 - Pneumococcal polysaccharide
 - o Hepatitis A
 - o Hepatitis B

- Meningococcal conjugate vaccine (MenACWY) and serogroup B meningococcal vaccine (MenB)
- Haemophilus influenzae type b
- Co-administered immunization (same list as history of immunizations)
- Residing in a nursing home*§
- * ICD-10-CM diagnosis codes, ICD-10-PCS codes, CPT, HCPCS procedure codes, or operational definition based on other data available in VHA's CDW will be provided in the SAP.

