9.7.3. Subgroup Analysis

Separate analyses of baseline characteristics and safety analyses in subgroups of interest may be conducted based on feasibility, sample size, and data availability. These analyses will be performed for all subgroups listed in Section 9.2.3 as applicable to each age group. For each subgroup, a new set of ATT weights will be generated in the comparison with contemporary vaccinated and unvaccinated controls, and analyses will be conducted as described above.

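### Against unvaccinated controls, co-administered vaccines cannot be balanced by the propensity weights, yet the covariate rule as written selects them

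*Protocol*

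**What the plan says.** Section 9.7.2.2 builds the propensity score by logistic regression on variables judged clinically important, together with "baseline covariates that have standardized differences ≥10% between the two cohorts". ABRYSVO recipients get weight one, and "ATT weights will be PS/(1-PS) for individuals with no record of ABRYSVO". Truncation is the only remedy named for extreme weights. Section 9.7.1 sets the balance criterion: "Standardized differences <10% will indicate that the characteristics between recipients of ABRYSVO and the comparator cohort are balanced".

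The Abstract ends its key covariates with "history of immunizations, and coadministered immunizations", and Section 9.3.3 lists "Co-administered immunization (same list as history of immunizations". Section 9.3.3 also calls the list provisional and leaves the final list to the SAP.

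For the unvaccinated control cohort (cohort C), Section 9.2.1 requires "No record for any other vaccine (eg, those listed in Section 9.3.3) on or within 30 days of the index date". Section 9.7.2.5 defines co-administration as ABRYSVO plus another vaccine on the same day. It gives no definition for controls.

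Section 9.2.3 makes co-administered recipients a subgroup in both age groups. Section 9.7.3 adds: "For each subgroup, a new set of ATT weights will be generated in the comparison with contemporary vaccinated and unvaccinated controls".

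**The concern.** A propensity score can balance a covariate only if both cohorts contain people at each of its levels. In the unvaccinated comparison this covariate is zero for every control by eligibility, while ABRYSVO recipients are a mixture. The entry rule nevertheless picks it up, because it looks only at the size of the imbalance and not at whether the imbalance can be removed.

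Two things are at stake. First, the weighted controls may no longer resemble the ABRYSVO arm on covariates that could have been balanced, so the estimate is not the effect among the treated that Section 9.7.2.2 aims for. Second, even with sound weights, ABRYSVO recipients who also had an influenza or COVID-19 vaccine that day are compared with people who had no vaccine. Section 9.9 reads the cohort comparison as risk due to ABRYSVO, and this contrast alone cannot support that reading.

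**Working it through.** **Inputs.** From the protocol: the 10% entry and balance rules (9.7.2.2, 9.7.1), the odds weight for controls (9.7.2.2), 0% other-vaccine receipt in cohort C (9.2.1) and 4:1 sampling of controls (9.5.1). The protocol gives no figure for the co-administered share p or for the atrial fibrillation rate ratio r of other vaccines. Both are assumed here: p = 20%, 40%, 60%; r = 1 to 1.5.

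**1. Does the rule select the variable?** For a binary covariate with proportion p against 0, the standardized difference is p / sqrt(p(1-p)/2) = sqrt(2p/(1-p)).

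- It equals 0.10 when 2p = 0.01(1-p), that is p = 0.01/2.01, about 0.5%.
- At p = 20%, 40%, 60% it is 0.71, 1.15, 1.73.

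The rule therefore selects it at any realistic p. The control proportion stays 0% under any weights, so the 10% balance criterion cannot be met.

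**2. What happens to the weights?** Every person with the covariate present is an ABRYSVO recipient, so the logistic model has quasi-complete separation. The fitted score tends to 1 for co-administered recipients, and the rest of the model is in effect fitted to ABRYSVO-alone recipients against controls. The control weights then sum to about the number of ABRYSVO-alone recipients.

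A simulation illustrates this. It used 40,000 recipients, 160,000 controls and one age-like covariate, with a mean 0.4 SD higher in recipients and associated with co-administration (log-odds 0.5 per SD). Realised shares were 21.3%, 40.5% and 59.4%.

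| p | Coefficient on co-administration | Sum of control weights | 40,000 × (1 - realised share) | Age-like SMD, covariate in | Age-like SMD, covariate out |
|---|---|---|---|---|---|
| 20% | 21.3 | 31,491 | 31,480 | 0.095 | -0.001 |
| 40% | 22.2 | 23,818 | 23,800 | 0.189 | 0.000 |
| 60% | 23.0 | 16,228 | 16,240 | 0.282 | 0.001 |

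The age-like imbalance is just inside the 10% criterion at 20% and outside it at 40% and 60%. It arises because age and co-administration are related in the simulation. Truncation does not help, since the fault is not a few extreme control weights.

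**3. What if the covariate is left out?** The control weights sum to about 40,000 (40,006, 40,002, 39,996) and the age-like covariate balances. Co-administration itself stays at SMD 0.74, 1.17, 1.71, so the contrast is still a mixture.

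**4. What could the mixture do to the hazard ratio?** With no ABRYSVO effect, HR = (1-p) + p·r.

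| r | p = 20% | p = 40% | p = 60% |
|---|---|---|---|
| 1.0 | 1.00 | 1.00 | 1.00 |
| 1.2 | 1.04 | 1.08 | 1.12 |
| 1.5 | 1.10 | 1.20 | 1.30 |

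In the co-administration subgroup p = 1, so HR = r: the effect of the other vaccine is fully confounded with that of ABRYSVO.

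**5. The vaccinated comparison.** The result depends on how co-administration is coded in these controls.

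- Any vaccine at index, counting the control's own: fixed at 100%, SMD = sqrt(2(1-p)/p) = 2.83, 1.73, 1.15. Cannot balance.
- The literal Section 9.7.2.5 definition: fixed at 0% in controls. Cannot balance.
- Separate indicators per vaccine type: no full separation, but simulated residual |SMD| of 0.13 to 0.78.
- A vaccine additional to the index vaccine: overlap exists, simulated SMD 0.01 to 0.02. Balances.

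**The case against.** The strongest reply is that nothing is forced. Section 9.3.3 calls the covariate list provisional and gives the final list to the SAP, which can drop or recode this variable without contradicting the protocol. That stands, so the point is what the rule does if applied as written, not that it must be applied that way. The grounds given for changing the list are feasibility and availability, however, and neither would flag a variable that is recorded and easy to derive. Dropping it also leaves the cohort contrast unchanged.

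It is also fair that this is the secondary comparator, that Section 9.7.3 makes subgroup analyses conditional, and that the same subgroup against vaccinated controls comes close to ABRYSVO plus another vaccine versus another vaccine. These limit the reach of the point. They do not answer it for the unvaccinated contrast.

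Two stronger readings are tempting. A reader might infer that separation affects both control groups. The documents do not support this, because coding in vaccinated controls is undefined and one natural coding balances well. A reader might also infer that the primary comparison is biased against finding harm, because the other vaccine's effect is subtracted there. Under a null ABRYSVO effect that hazard ratio is ((1-p) + p·r)/r. The co-administered part contributes p·r/r = p and cancels. What remains is ABRYSVO alone against another vaccine, which is the intended active-comparator contrast, and it departs from 1 only if r does. The protocol gives no value for r.

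**Conclusion.** The point holds for the secondary comparison with unvaccinated controls. The protocol's covariate list, entry rule and eligibility criteria together select a variable that cannot be balanced once more than about 0.5% of recipients are co-administered. The structural result needs no assumption beyond that share. The loss of balance on other covariates depends on their being associated with co-administration; its size here is illustrative.

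Removing the covariate cures the weights but not the mixed contrast, and the co-administration subgroup against unvaccinated controls cannot separate ABRYSVO from the vaccine given with it. Any distortion of the hazard ratio (1.04 to 1.30 under a null effect for p of 20% to 60% and r of 1.2 to 1.5) rests on assumed values and is zero at r = 1. For the primary comparison, the supported finding is only that co-administration needs a definition in controls.

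**What to change.** For the unvaccinated comparison:

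- Exclude co-administered immunizations from the propensity candidates, stated as an exception to the 10% rule.
- Run the comparison, or at least a stated parallel analysis, in ABRYSVO recipients without a same-day vaccine.
- Drop the co-administration subgroup from this comparison and keep it against vaccinated controls.

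For the vaccinated comparison, either define co-administration in controls as a vaccine additional to the index vaccine, or keep the variable out of the propensity model. Reporting ABRYSVO plus vaccine X against X alone is an optional addition.

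The data are already collected, so the change is wording plus one restriction. The cost is a smaller ABRYSVO arm against unvaccinated controls. To keep the 37,444 recipients that Table 2 gives for a 2-fold increase at age 60 and over (4:1), the total needed is 37,444/(1-p): 46,805, 62,407 or 93,610 at p = 20%, 40% or 60%.
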